5.7.3. Additional Safety Assessments**5.7.3.1. Clinical Laboratory Tests**

Clinical laboratory tests will be displayed for the participants included in the safety analysis set.

Descriptive statistics and graphical displays will be presented for selected chemistry and hematology, laboratory tests at scheduled time points.

Change from baseline through Week 24 and Week 52 will be summarized for chemistry and hematology tests and displayed by intervention group. A box plot of change from baseline through Week 24 and Week 52 will be provided.

- **Hematology assessments** will include but are not limited to the following: hemoglobin, hematocrit, platelet count, total and differential White Blood Cell count, B-cell analysis.
- **Blood chemistry assessments** will include but are not limited to the following: chemistry panel (total and direct bilirubin, alanine aminotransferase, aspartate aminotransferase, alkaline phosphatase, albumin, total protein, calcium, phosphate, sodium, potassium, chloride, blood urea nitrogen/urea, and creatinine).

The National Cancer Institute's Common Terminology Criteria for Adverse Events (NCI-CTCAE; version 5.0) will be used in the summary of laboratory data (Grade 0-4). The proportion of participants with post-baseline values by maximum toxicity grade for clinical laboratory tests will be summarized by study intervention group. Participants with toxicity grades ≥ 2 will be listed.

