Alkaline phosphatase increased	>ULN - 2.5 x ULN if baseline was normal; 2.0 - 2.5 x baseline if baseline was abnormal	>2.5 - 5.0 x ULN if baseline was normal; >2.5 - 5.0 x baseline if baseline was abnormal	>5.0 - 20.0 x ULN if baseline was normal; >5.0 - 20.0 x baseline if baseline was abnormal	>20.0 x ULN if baseline was normal; >20.0 x baseline if baseline was abnormal	Ranges defined for "abnormal baseline" are applied only if baseline > ULN. If baseline < LLN, then ranges for "normal baseline" are applied.
Aspartate aminotransferase increased	>ULN - 3.0 x ULN if baseline was normal; 1.5 - 3.0 x baseline if baseline was abnormal	>3.0 - 5.0 x ULN if baseline was normal; >3.0 - 5.0 x baseline if baseline was abnormal	>5.0 - 20.0 x ULN if baseline was normal; >5.0 - 20.0 x baseline if baseline was abnormal	>20.0 x ULN if baseline was normal; >20.0 x baseline if baseline was abnormal	Ranges defined for "abnormal baseline" are applied only if baseline > ULN. If baseline < LLN, then ranges for "normal baseline" are applied.

CTCAE Term	Grade 1	Grade 2	Grade 3	Grade 4	Janssen implementation notes
Blood bilirubin increased	>ULN - 1.5 x ULN if baseline was normal; > 1.0 - 1.5 x baseline if baseline was abnormal	>1.5 - 3.0 x ULN if baseline was normal; >1.5 - 3.0 x baseline if baseline was abnormal	>3.0 - 10.0 x ULN if baseline was normal; >3.0 - 10.0 x baseline if baseline was abnormal	>10.0 x ULN if baseline was normal; >10.0 x baseline if baseline was abnormal	Ranges defined for "abnormal baseline" are applied only if baseline > ULN. If baseline < LLN, then ranges for "normal baseline" are applied.
CD4 lymphocytes decreased	<LLN - 500/mm ³ ; <LLN - 0.5 x 10e9/L	<500 - 200/mm ³ ; <0.5 - 0.2 x 10e9/L	<200 - 50/mm ³ ; <0.2 x 0.05 - 10e9/L	<50/mm ³ ; <0.05 x 10e9/L	
Cholesterol high	>ULN - 300 mg/dL; >ULN - 7.75 mmol/L	>300 - 400 mg/dL; >7.75 - 10.34 mmol/L	>400 - 500 mg/dL; >10.34 - 12.92 mmol/L	>500 mg/dL; >12.92 mmol/L	
CPK increased	>ULN - 2.5 x ULN	>2.5 x ULN - 5 x ULN	>5 x ULN - 10 x ULN	>10 x ULN	
Creatinine increased	Creatinine Kinase >ULN - 1.5 x ULN	Creatinine Kinase >1.5 - 3.0 x baseline; >1.5 - 3.0 x ULN	Creatinine Kinase >3.0 x baseline; >3.0 - 6.0 x ULN	Creatinine Kinase >6.0 x ULN	

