Hypokalemia	Potassium <LLN - 3.0 mmol/L	Symptomatic with Potassium <LLN - 3.0 mmol/L; intervention indicated	Potassium <3.0 - 2.5 mmol/L; hospitalization indicated	Potassium <2.5 mmol/L; life-threatening consequences	“Symptomatic” ranges are applied for grade 2, grade 1 not assigned, i.e. worst case applied. Clinical signs and symptoms are not taken into consideration for grading of grade 3 and 4.
Hypomagnesemia	Magnesium <LLN - 1.2 mg/dL; <LLN - 0.5 mmol/L	Magnesium <1.2 - 0.9 mg/dL; <0.5 - 0.4 mmol/L	Magnesium <0.9 - 0.7 mg/dL; <0.4 - 0.3 mmol/L	Magnesium <0.7 mg/dL; <0.3 mmol/L; life-threatening consequences	Clinical signs and symptoms are not taken into consideration for grading.

CTCAE Term	Grade 1	Grade 2	Grade 3	Grade 4	Janssen implementation notes
Hyponatremia	Sodium <LLN - 130 mmol/L	Sodium 125-129 mmol/L and asymptomatic	Sodium 125-129 mmol/L symptomatic; 120-124 mmol/L regardless of symptoms Sodium <130-120 mmol/L	Sodium <120 mmol/L; life-threatening consequences	Clinical signs and symptoms are not taken into consideration for grading. Worst case (“<130-120 mmol/L” for grade 3 added by Janssen) is applied across grade 2/3 ranges: 120-129 mol/L assigned to grade 3, grade 2 not used.

* Grade 0 is assigned to a lab assessment when the lab test is described in the table, but the lab value is not assigned a grade 1 or higher.

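### SAP Appendix 10 names creatinine kinase where serum creatinine should be graded, and its white-cell SI limits contradict the per-mm³ limits beside them

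*SAP*

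**What the plan says.** Protocol 9.4.6 leaves the CTCAE grades to the SAP, and SAP Appendix 10 is where they are specified.

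- **Creatinine row.** Under the term *Creatinine increased* the four cells read "Creatinine Kinase >ULN - 1.5 x ULN" (Grade 1), "Creatinine Kinase >1.5 - 3.0 x baseline; >1.5 - 3.0 x ULN" (Grade 2), "Creatinine Kinase >3.0 x baseline; >3.0 - 6.0 x ULN" (Grade 3) and "Creatinine Kinase >6.0 x ULN" (Grade 4). The row above, *CPK increased*, has cut-offs of 1, 2.5, 5 and 10 x ULN; its Grade 2 cell is ">2.5 x ULN - 5 x ULN". Creatinine belongs to the safety chemistry panel, whose list in SAP 5.7.3.1 ends with "blood urea nitrogen/urea, and creatinine". Protocol Appendix 8 lists creatinine and creatine phosphokinase as separate tests.
- **White-cell row.** Under *White blood cell decreased*, Grade 2 gives 3000 to 2000 per mm³ beside <2.0 x 10e9/L. Grade 3 gives 2000 to 1000 per mm³ beside <1.0 x 10e9/L. Grade 4 gives <1000 per mm³ beside <1.0 x 10e9/L.
- **Default.** The footnote provides that "Grade 0 is assigned to a lab assessment when the lab test is described in the table" but the value reaches no higher grade.
- **Use.** Maximum CTCAE grade for hematology and chemistry is a secondary safety endpoint (SAP 1.1). SAP 5.7.3.1 states that post-baseline values "by maximum toxicity grade for clinical laboratory tests will be summarized by study intervention group" and lists participants at Grade 2 or above. SAP 5.7 keeps all safety analyses for the CSR.

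**The concern.** These cells are operating thresholds that a programmer will code. In the creatinine row, the term and the analyte named in the cells disagree, and the analyte named is close to one that is measured and graded elsewhere. In the white-cell row, two cells carry limits in two units that cannot both be right, and the SI limits for Grades 3 and 4 are identical.

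At stake are the by-arm table of maximum grade and the Grade 2 or higher listing. A value pushed down to Grade 0 or 1 disappears from the listing, and a test without a grade never enters it. The trial is small: the original target was about 30 per arm and fewer than 60 will be enrolled. If the arms are near equal, one misgraded participant moves an arm's proportion by at least about 1/30 = 3.3 percentage points.

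**Working it through.** **1. Conversion rule, tested on the table itself.** A count of 1000/mm³ equals 1.0 x 10e9/L, so SI limit = (limit per mm³)/1000. Applied to Grades 2 to 4 of the lymphocyte (decreased), neutrophil, platelet and CD4 rows, this reproduces all 4 x 3 = 12 cells. Neutrophils Grade 2, for instance: 1500/1000 = 1.5 and 1000/1000 = 1.0, as printed. CD4 Grade 3 is read as 0.2 to 0.05, because its multiplication sign and dash are swapped in print.

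**2. White-cell row.**

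| Grade | Per mm³ | Converted (x 10e9/L) | Printed SI | Agree? |
|---|---|---|---|---|
| 1 | LLN to 3000 | LLN to 3.0 | LLN to 3.0 | yes |
| 2 | <3000 to 2000 | <3.0 to 2.0 | <2.0 | no |
| 3 | <2000 to 1000 | <2.0 to 1.0 | <1.0 | no |
| 4 | <1000 | <1.0 | <1.0 | yes |

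**3. Values graded by each set of limits.**

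| Value (x 10e9/L) | By mm³ limits | By SI limits alone |
|---|---|---|
| 2.9, 2.5, 2.0 | 2 | no cell met, so 0 |
| 1.9, 1.5, 1.0 | 3 | 2 |
| 0.9, 0.5 | 4 | 2, 3 and 4 all met; maximum 4 |

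So 2.0 to <3.0 loses two grades and leaves the Grade 2 or higher listing. The band 1.0 to <2.0 loses one grade. Below 1.0 the maximum grade is still right.

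**4. Creatinine row read literally, against the CPK row.** The cut-offs are 1, 1.5, 3 and 6 x ULN in the creatinine row and 1, 2.5, 5 and 10 x ULN in the CPK row.

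| Kinase (x ULN) | CPK row | Creatinine row |
|---|---|---|
| 1.2 | 1 | 1 |
| 2 | 1 | 2 |
| 2.6 | 2 | 2 |
| 4 | 2 | 3 |
| 5.5 | 3 | 3 |
| 7 | 3 | 4 |
| 11 | 4 | 4 |

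The two rows disagree by one grade above 1.5 up to 2.5, above 3 up to 5, and above 6 up to 10 x ULN. The creatinine row also has limits relative to baseline, which the CPK row lacks. No remaining row grades serum creatinine, so under the literal reading it is ungraded at every level.

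**The case against.** The strongest reply is that neither slip need do harm.

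- **Creatinine.** The row term is creatinine, Protocol Appendix 8 has no test called creatinine kinase, the multiples differ from those for CPK, and both SAP 5.7.3.1 and Appendix 10 name CTCAE v5.0 as the scale. A programmer would probably see a stray word. This stands: the harm arises only if the cells are coded as written. But a silent repair would leave the specification wrong and the correction undocumented.
- **White cells.** The per-mm³ limits are coherent at every grade, and 2.5 x 10e9/L is 2500/mm³, which meets Grade 2 there. Grading per mm³, or taking the worse grade over both units, gives the right answer. This stands too. The plan does not state either rule, however. Appendix 10 spells out worst-case grading where it uses it (lipase, amylase, potassium, sodium), and the notes cells for these two rows are empty. Protocol exclusion criteria 13 and 14 give neutrophil and platelet limits in x 10^9/L, which shows that SI units are in use but does not settle how white cells are graded.
- **Conversion of the PDF.** A lost range start in two cells cannot be excluded outright, and the CD4 cell shows some disorder in an SI string. Loss is unlikely, because the same row's Grade 1 cell and the neighbouring count rows keep both ends.
- **Grey italic text is not applied.** The affected cells show no such marking.

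Other information also remains. SAP 5.7.3.1 summarises change from baseline in chemistry and hematology, naming creatinine and white-cell count, without using Appendix 10. Neutrophils and lymphocytes have consistent rows, and Protocol 8.2.4 requires clinically relevant laboratory changes to be recorded as adverse events.

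**Conclusion.** Both errors are in the current SAP and can be shown from the table alone. They affect six cells: four naming the wrong analyte, and two whose SI limits contradict the per-mm³ limits. The consequence is conditional. If the creatinine cells are coded literally, serum creatinine has no grade and the enzyme has two that can conflict. If the white-cell SI limits are applied alone, values from 1.0 to below 3.0 x 10e9/L are under-graded by one or two grades.

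A reader might infer more than this, and the documents do not support it:

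- That renal toxicity and low white-cell counts will be misgraded in the CSR. The documents do not say how the cells or units are programmed.
- That the error favours one arm. The same table applies to both.
- That eGFR appears only inside complete renal response, so that creatinine grading is the sole renal check. eGFR is also an exclusion criterion (Protocol 5.2), a baseline characteristic (SAP Appendix 3) and a listed subgroup variable (SAP 5.8.5, although that analysis is not kept for the CSR).
- That the plan identifies leukopenia as a central risk. For combined immunosuppression, the risk table in Protocol 2.3.1 names infection and malignancy.

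The primary analysis, alpha and power are untouched. The point is worth correcting because a reported safety endpoint depends on these thresholds. It does not threaten the trial's main conclusion.

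**What to change.** Before database lock, correct Appendix 10:

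- In the four *Creatinine increased* cells, name serum creatinine and keep the printed multiples. Leave creatine kinase to *CPK increased*.
- In *White blood cell decreased*, set the SI limits to <3.0 - 2.0 x 10e9/L (Grade 2) and <2.0 - 1.0 x 10e9/L (Grade 3). Grades 1 and 4 are already right.
- Check the grading program against the corrected cells, using a few test values such as 2.5 and 1.5 x 10e9/L and a creatinine of 2 x ULN, and record the correction in the SAP version history.

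The cost is six table cells and a short program check. No new data are needed, and no other analysis changes.
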